LARS and the Fecal Incontinence Quality of Life Instrument		X		X			6, 12, 24 and 36		
Health Economics									
EQ-5D-5L		X	X ¹⁹	X		X	6, 12, 24 and 36		
Phone Contact									
Survival information								X	X
1. Timing for visits after excision are scheduled from last tumour excision date: a. For patients having TME as first protocol excision: from TME date b. For patients having TEMS/TAMIS as first protocol excision: from TEMS/TAMIS date c. For patients having TEMS/TAMIS as first protocol excision and then having a TME: from TME date 2. See protocol section 8 for definitions. 3. Phone contacts or visits after first disease relapse are required every 6 months from date of relapse. 4. Tests may be done on the date of treatment or, if not possible, the previous working day before treatment day. If treatment is to begin on a Monday, may be done on the previous Friday (maximum 72 hours prior to treatment). 5. Please also see protocol Section 12.0 and details for collection, processing, storing, and shipping these samples provided in the CO.28 Correlative Studies Manual. 6. Whole blood (that is not for ctDNA testing) will only be collected prior to enrollment. 7. Not required for patients that had a TME. 8. To be obtained within 28 days as close to the time of relapse as possible. Blood for correlatives done within 28 days PRIOR to date of relapse does not need to be repeated. 9. For CT pelvis and chest, a CT scan with contrast is preferred but not mandated. Patients with contrast allergies may undergo chest X-ray and /or Chest MRI. 10. Contrast is REQUIRED for the CT scan of the abdomen. Patients with contrast allergies may undergo liver ultrasound and /or MRI. 11. Rectal exam and proctoscopy are ideally to be performed by the primary surgeon. Proctoscopy should be performed ≤ 90 days prior to enrollment. Ideally, the surgeon should perform pre and post induction treatment proctoscopies. A gastroenterologist may perform proctoscopy in lieu of the surgeon, but then must also perform the follow-up exam. Proctoscopy may be accomplished using rigid proctoscopy or as part of a flexible sigmoidoscopy or colonoscopy. 12. For patients that had a TME it is only required at month 36. 13. If a rectal tumour tissue biopsy was performed within 90 days prior to enrollment, a repeat biopsy is not necessary. It is recommended that surgeons take a biopsy of the tumour during sigmoidoscopy/colonoscopy to ensure tissue availability and adequate pathology report confirming invasive well-moderately differentiated rectal adenocarcinoma and no evidence of pathologic high risk factors. 14. It is strongly encouraged that suspicious or unequivocal evidence of first local relapse be confirmed definitively by either biopsy (preferred) or by repeat/confirmatory imaging. Where imaging evidence of first local relapse is, in the opinion of the investigator and radiologist, absolutely unequivocal and not requiring subsequent confirmation by either biopsy or follow-up imaging, this must be clearly indicated in supporting documentation. 15. Urine pregnancy test in women of childbearing potential and if a false-positive is suspected this may include an ultrasound to rule-out pregnancy. 16. To be completed daily for patients receiving Capecitabine. 17. Adverse Events to be evaluated using the NCI Common Terminology Criteria for Adverse Events (CTCAE v5.0) (see Appendix III). 18. Only protocol chemotherapy or surgery related adverse events have to be reported after the 30 days post-excision visit. 19. After 3 cycles of FOLFOX or after 2 cycles of CAPOX.									

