8.7 Disease Free Survival

Disease-Free Survival (DFS) is defined as the interval from complete tumour surgical excision date (with pathology results negative for malignant disease within 1 mm of surgical margins) to date of first occurrence of the events in the table below.

Patients not meeting the criteria for failure by the analysis data cutoff date will be censored at their last disease assessment date.

First Event	Disease Free Survival
None	Censored
Locoregional relapse	Failure
Distant disease	Failure
Non-protocol radiotherapy, chemotherapy or biologic therapy without documentation of the site of failure	Failure
Death due to any other reason	Failure

8.7.1 Capture of Failures and Work-up at Detection of First Failure:

Only the first event experienced will determine a patient's failure status for DFS analysis. However, in order to fully capture the patterns of failure in this study population, a detailed work-up at the time of the first failure is required, and sites of failures should be documented in the CRF.

For instance, if a patient first develops locoregional relapse, then a work-up for distant metastasis will be performed at the same time. If the distant metastatic work-up reveals the presence of distant metastasis, then all sites of failure will be documented, even though the time of the first detected failure event will be used to determine the disease free survival. Similarly, if a patient is first found to have distant metastasis, then a work-up for locoregional relapse should be performed at the same time. If the locoregional work-up does not reveal relapse at the same time, then this patient is considered to only have distant disease failure.

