7.1 General Methods

Continuous and ordinal categorical variables are summarized using the mean, median, standard error, minimum and maximum values. All confidence intervals are computed based on normal approximations except those for rates, which will be computed based on the exact method.

Percentages given in the summary tables will be rounded and may therefore not always add up to exactly 100%. Listings, tabulations, and statistical analyses will be carried out using the SAS (Statistical Analysis System, SAS Institute, North Carolina, USA) software.

Baseline evaluations will be those collected on CRF Eligibility Worksheet and Baseline Report and closest to, but no later than, the first day of study medication for treated subjects and closest to, but no later than, the date of enrollment, for subjects who were enrolled but who never received any treatment.

Laboratory results, adverse events, and other symptoms are coded and graded using the NCI CTCAE when available.

When converting a number of days to other units, the following conversion factors will be used:

1 year = 365.25 days

1 month = 30.4375 days

When either day or month of a date is missing, the missing day and/or month will be imputed by the midpoint within the smallest known interval. For example, if the day of the month is missing for any date used in a calculation, the 15th of the month will be used to replace the missing day. If the month and day of the year are missing for any date used in a calculation, the first of July of the year will be used to replace the missing date.

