Kaplan-Meier method (**Figure 2**) will be used to estimate the 3 year loco-regional relapse rate and associated 95% confidence interval first among all patients treated with FOLFOX or CAPOX and TEMS or TAMIS (**Table 31**) and additionally among all patients that have received neoadjuvant chemotherapy.

7.7.3 3 Year Distant Relapse Rate

Distant relapse is defined as appearance of rectal cancer disease at sites remote from the rectum. The number of patients with each site of distant relapse (Lung, Liver, Brain, Distant lymph nodes, Bone, Skin, Ascites, Pleural effusion, Adrenal glands, Other) will be summarized (**Table 31**).

Distant relapse free survival is calculated as time from complete tumour surgical excision date (with pathology results negative for malignant disease within 1 mm of surgical margins) to the first date of definitive evidence (clinical, radiological or pathological) of distant relapses. Patients died, loss to follow up, or alive at clinical cut-off will be censored at respectively date of death, date of lost to follow-up, and last disease assessment date calculated as the last of dates of attendance/last contact on CRD Follow-up Report.

Kaplan-Meier method (**Figure 3**) will be used to estimate the 3 year distant relapse rate and associated 95% confidence interval first among all patients treated with FOLFOX

or CAPOX and TEMS or TAMIS (**Table 31**) and additionally among all patients that have received neoadjuvant chemotherapy.

7.7.4 3 year Disease Free Survival

Disease-Free Survival (DFS) is defined as the interval from complete tumour surgical excision date (with pathology results negative for malignant disease within 1 mm of surgical margins) to date of first occurrence of the events in the below.

- Locoregional relapse reported in CRF Relapse Report
- Distant disease reported in CRF Relapse Report
- Non-protocol radiotherapy, chemotherapy, or biologic therapy without documentation of the site of failure and reported in CRF Chemotherapy Report, Pre-Excision Report, and Surgery Report
- Death due to any other reason reported in CRF Death Report

Patients who are alive without locoregional or distant relapse or receiving non-protocol radiotherapy, chemotherapy, or biologic therapy without documentation of the site of failure at the analysis data cutoff date will be censored at their last disease assessment date calculated as the last of dates of attendance/last contact on Follow-up Report.

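### The 3-year relapse and DFS rates are read on the same day as the nominal month-36 assessment, with no visit window, so relapses first found at a late month-36 visit drop out of the estimate; the time origin after two excisions is also not fixed

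*SAP*

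**What the plan says.** **Event clock.** SAP 7.7.3 states: "Distant relapse free survival is calculated as time from complete tumour surgical excision date". An excision is complete when it is one "with pathology results negative for malignant disease within 1 mm of surgical margins". SAP 7.7.2 uses the same origin for locoregional relapse, as do SAP 7.7.4 and Protocol 8.7 for DFS: "Disease-Free Survival (DFS) is defined as the interval from complete tumour surgical excision date".

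**Read-out.** In SAP 7.7.3 the Kaplan-Meier method "will be used to estimate the 3 year distant relapse rate"; 7.7.2 and 7.7.4 do the same for their endpoints. No tolerance around the 3-year point is stated. SAP 7.1 sets "1 year = 365.25 days" and "1 month = 30.4375 days".

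**Visit clock.** In the Protocol 5.0 flowsheet, CT of chest and abdomen after excision is scheduled at months 12, 24 and 36. Pelvic MRI is at months 6, 18 and 30, and endoscopy is at every six-monthly visit. After TME the MRI is not required, and footnote 12 says of endoscopy: "For patients that had a TME it is only required at month 36". No window is given for follow-up visits or scans. Footnote 1 counts visits from the last excision; for two-excision patients it reads: "For patients having TEMS/TAMIS as first protocol excision and then having a TME: from TME date". Protocol 7.3 and SAP 7.7.1 place that TME 6-8 weeks after the local excision.

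TEMS/TAMIS-then-TME patients belong to the main analysis set for these endpoints (SAP 6, set 3).

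**The concern.** An assessment scheduled on the very day at which the curve is read has no slack. If it happens a few days late, what it finds is dated after 3 years and the Kaplan-Meier estimate at 3 years ignores it. For distant disease the month-36 CT is the only scheduled scan for relapse arising after month 24, so much of the third year can depend on it. The error runs one way: relapse rates too low, DFS too high.

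There is a second gap for patients who have TEMS/TAMIS and then TME. Their visits are timed from TME. Their event clock may start earlier, because a local excision specimen with a clear margin (a ypT2 tumour, for example) already meets the written definition of complete excision. Neither document says which of the two dates applies.

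**Working it through.** The plan gives no target, event count or precision for the 3-year endpoints, so there is no stated figure to reproduce.

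**1. Do the two days coincide?** With the SAP 7.1 factors, 3 × 365.25 = 1095.75 days and 36 × 30.4375 = 1095.75 days. In calendar terms, a third anniversary that spans 29 February 2020 is 1096 days (1096/365.25 = 3.0007 years, just outside). For an excision after that date it is 1095 days (2.998 years, counted). Adding one day, as the follow-up formula in SAP 7.2.1 does, would put both outside (1096 and 1097 days).

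**2. Two-excision patients.** If the clock starts at TEMS/TAMIS, a TME 42 to 56 days later moves month 36 to 36 + 42/30.4375 = 37.4 months up to 36 + 56/30.4375 = 37.8 months. If the clock starts at TME, there is no shift.

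**3. Size for distant relapse, closed form.** Assumptions not in the documents: constant hazard, and every relapse found by scheduled CT only. With true 3-year rate F, the share arising by month 24 is 1 − (1 − F)^(24/36). If a fraction q of month-36 scans are on time, the estimate is that share plus q times the remainder.

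- F = 10%: by month 24, 1 − 0.9^(2/3) = 6.8%. All late: 6.8%. Half late: 6.8 + 0.5 × 3.2 = 8.4%. None late: 10%.
- F = 5%: all late 3.4%, half late 4.2%.
- F = 20%: all late 13.8%, half late 16.9%.

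**4. Simulation.** The assumptions of step 3 were used with 50 patients, 1,500 runs, scan dates uniform over the range shown, a TEMS-to-TME gap of 42-56 days and a true rate of 10%:

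| Scan timing | No two-excision patients | Half, clock from TEMS | Half, clock from TME |
|---|---|---|---|
| 0-28 days early | 9.9% | 8.5% | 10.0% |
| within ±28 days | 8.4% | 7.7% | 8.4% |
| 0-28 days late | 7.0% | 7.2% | 7.1% |

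The half-share is the design's 50% organ preservation rate turned round; the actual share is not in the documents. Read at 39 months with the TEMS clock, the same runs give 9.9% to 10.5%.

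**5. Locoregional relapse under surveillance.** These patients have MRI and endoscopy at month 30. If that look finds everything then present, only relapse arising after month 30 is at stake. At a true 10%, 1 − 0.9^(30/36) = 8.4% if all month-36 looks are late, and (8.4 + 10)/2 = 9.2% if half are.

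**6. Dating of relapse.** SAP 7.7.2 and 7.7.3 date a relapse at definitive evidence, while Protocol 8.6 uses the first suspicious record. Under the SAP rule, a suspicious month-36 scan confirmed weeks later moves further past 3 years.

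**The case against.** A reader might infer that the month-36 scan always falls on or after the 3-year day. The documents do not support this. Without a window, early scans are allowed, and Kaplan-Meier counts any event dated at or before 3 years; step 4 recovers 9.9% when scans are up to 28 days early and no patient has two excisions. A scan on the exact anniversary may count or not, depending on the leap day.

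Nor can it be said that two-excision patients with a clear TEMS margin are always late. That needs the TEMS date as origin and a scan not 6-8 weeks early. The TME date is not ruled out, and choosing it removes the shift. What stands is that the origin is ambiguous.

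The CT-only sizes should not be carried over to locoregional relapse or DFS. Physical examination and CEA are scheduled every six months for everyone, and MRI and endoscopy are added for patients who keep the rectum. Relapses found between scans are unaffected.

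The stakes are also limited. These endpoints are descriptive, with no threshold, and the trial's success rests on organ preservation. In 50 patients a true 10% is 5 relapses, with an exact 95% interval of 3.3% to 21.8%. Reading 8.4% or 6.8% instead is a shift of 0.8 or 1.6 patients. No relapse disappears from Table 31 or the curves.

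All of this narrows the point without removing it. The bias has one direction, it affects the reported 3-year figures, and a rule written in advance avoids it.

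**Conclusion.** The concern holds in limited form. The 3-year read-out coincides with the nominal month-36 assessment, no window is given, and relapses first found at a late month-36 visit are missing from the 3-year estimates. For distant relapse, a true 10% reads about 8.4% if half the scans are late and 6.8% if all are. That rests on constant hazard, CT-only detection and an assumed share of late scans, none of which the documents give. The loss is smaller for locoregional relapse under surveillance and for relapses found between scans.

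For TEMS/TAMIS-then-TME patients the time origin is unspecified. On the TEMS reading their month 36 falls at about 37.4-37.8 months; on the TME reading the clocks agree. It is a modest favourable bias in descriptive oncological endpoints, worth correcting because doing so is cheap.

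**What to change.** In SAP 7.7.2-7.7.4:

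1. Pre-specify that a relapse first detected at the month-36 assessment counts as within 3 years. State a visit window for the analysis and assign event and censoring times to the nominal visit. Say whether the suspicious scan or its later confirmation fixes the visit, so that the SAP agrees with Protocol 8.6.
2. Add a reading of the curve after the window closes (39 months, for example) as a sensitivity analysis only. It is not strictly a 3-year rate, it overshoots slightly in some scenarios (up to 10.5% for a true 10%), and it may be unstable if many patients are censored at month 36.
3. State one time origin for two-excision patients, consistent with the visit clock in footnote 1c. Count any relapse or death between TEMS/TAMIS and TME as an event. Without that rule, moving the origin to TME would place such events before time zero and create a new favourable bias.

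The cost is SAP wording, a few lines of code and matching wording in Protocol 8.4 and 8.7, with no new visits or data. The relapse rates become slightly less favourable. The rule should be settled before the month-36 results are analysed.

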7.1.1 Drug Administration

7.1.1.1 **FOLFOX (5-fluorouracil + leucovorin + oxaliplatin)**

Agent(s)	Dose	Route	Duration	Schedule
Oxaliplatin	85 mg/m ²	IV over 2 hours	Day 1	Repeat every 14 days for a total of 6 cycles
Leucovorin	400 mg/m ² bolus	IV over 2 hours	Day 1	Repeat every 14 days for a total of 6 cycles
5FU	400 m/m ² bolus over 5 - 15 minutes then 2400 mg/m ² continual infusion over 46 - 48h total dose	IV	Days 1 to 2	Repeat every 14 days for a total of 6 cycles

1. Oxaliplatin could be administered first, prior to leucovorin; or concurrently with leucovorin administered via separate infusion containers.
2. If necessary to accommodate holidays, patient schedule or other justified circumstance, the schedule may be delayed up to 7 days.
3. Patients who cannot tolerate six cycles of FOLFOX or those that require dose modification below dose level -2 (see Section 7.1.3.1) may receive preoperative 5FU chemoradiotherapy based on investigator decision. If chemoradiotherapy is given, it should be given according to local institutional guidelines for FOLFOX administration. There are no restrictions on dose modifications for the 6th cycle of neoadjuvant FOLFOX.
4. Alternate folinic acids (i.e. levo-leucovorin) may be substituted for Leucovorin if not available. Note: Levo-leucovorin is twice as potent as leucovorin; dosages should be adjusted accordingly. Dosages are at the discretion of the treating physician. Dose modifications of leucovorin up to and including omission of leucovorin or its analogues imposed by drug shortages will not constitute protocol violations.
5. The dose modification schema for FOLFOX (see Section 7.1.3.1) is suggested. Oncologists may use clinical judgment in making dose modifications that deviate from the suggested schema. These will not constitute protocol violations.

7.1.1.2 ***CAPOX (capecitabine + oxaliplatin)***

Agent(s)	Dose	Route	Duration	Schedule
Capecitabine	1000 mg/m ² BID	PO	14 days starting on Day 1	Repeat every 21 days for a total of 4 cycles
Oxaliplatin	130 mg/m ²	IV over 2 hours	Day 1	Repeat every 21 days for a total of 4 cycles

1. Patients must be counseled about the importance of compliance with capecitabine. Compliance, with mention of missed doses, must be documented in the patient's medical record by site study personnel.
2. Missed doses must be documented on the appropriate CRF and by patients on their provided diary.

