APPENDIX III - DOCUMENTATION FOR STUDY

Follow-up is required for patients from the time of enrollment and will apply to all eligible and ineligible patients. This trial will use a web-based Electronic Data Capture (EDC) system for all data collection including SAE reporting (see Section 9.0 for details regarding SAE reporting). For details about accessing the EDC system and completing the on-line Case Report Forms, please refer to the Data Management Guidebook posted on the CO.28 area of the CCTG web-site (www.ctg.queensu.ca).

The ELECTRONIC CRFs to be used in this trial are:

Electronic Case Report Form	To be Completed/Submitted Electronically:	Supporting Documentation to be sent using Supporting Document Upload Tool*
BASELINE REPORT	Due within 2 weeks of patient enrollment.	Copies of signature pages of main and optional consent forms; relevant pathology & radiology reports.
CHEMOTHERAPY REPORT	To be completed after each chemotherapy cycle. Due within 2 weeks of end of cycle. This report documents treatment, adverse events and investigations for each chemotherapy cycle.	Relevant radiology reports.
PRE-EXCISION VISIT REPORT	To be complete within 2 weeks after pre-excision visit.	Relevant radiology reports.
END OF TREATMENT REPORT	To be complete within 4 weeks after final tumour excision	
SURGERY REPORT	To be complete within 4 weeks after surgery (either TME or TEMS/TAMIS)	Relevant pathology and surgery reports.
CORRELATIVE STUDIES	See Section 12 in this protocol.	Relevant pathology reports.
FOLLOW-UP REPORT	Continued follow-up after chemotherapy, radiotherapy and/or protocol tumour excision(s) completed. Due within 2 weeks after contact with patient.	Relevant pathology, radiology and surgery reports.
RELAPSE REPORT	To be completed at the time of disease relapse or failure. Due within 2 weeks after contact with patient.	Relevant pathology, radiology and surgery reports.
SHORT FOLLOW REPORT	To be completed after disease relapse or failure and for patients that have no protocol tumour excision.	
DEATH REPORT**	Required for all patients while study is open. Due within 2 weeks of knowledge of death.	Autopsy report, if done.

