7.7 Efficacy

7.7.1 Organ Preservation Rate

After completion of neoadjuvant chemotherapy, the protocol requires that patients with lesions that on pre-excision (post-chemotherapy) MRI and/or endoscopy showing evidence of progression or no response to chemotherapy to be treated with immediately

the radical TME surgery. Other patients will be treated with local excision TEMS or TAMIS. Patients with ypstage T0/T1goodN0 tumours based on local pathology ypstaging review after TEMS or TAMIS are treated with surveillance while patients with tumours with ypT2, N+ or ypT1 tumours with poor prognostic features are treated with radical TME surgery within 6-8 weeks after local excision. The numbers of enrolled patients who were treated with respectively neoadjuvant chemotherapy, TME and TEMS or TAMIS immediately after completion of neoadjuvant chemotherapy, and TME or surveillance after TEMS or TAMIS will be summarized (**Table 30**).

Organ preservation rate, the primary endpoint of this study, is defined as the proportion of patients with tumour downstaging to ypT0/T1good N0 who avoid radical surgery (TME) among all patients treated with FOLFOX or CAPOX and TEMS or TAMIS. The 95% confidence interval for the organ preservation rate will be calculated (**Table 30**).

Organ preservation rate will additionally be calculated among all patients that have received neoadjuvant chemotherapy.

7.7.2 3 Year Loco-Regional Relapse Rate

Locoregional relapse is defined as reappearance of a tumour within the rectum or pelvis. The number of patients with each site (rectum, pelvis, pelvic lymph nodes, and others) of locoregional relapse will be summarized (**Table 31**).

Locoregional relapse free survival is calculated as time from complete tumour surgical excision date (with pathology results negative for malignant disease within 1 mm of surgical margins) to the first date of definitive evidence (clinical, radiological or pathological) of locoregional relapses. Patients with distant relapse only, died, loss to follow up, or alive at clinical cut-off will be censored at respectively last date of distant relapses, date of death, date of lost to follow-up, and last disease assessment date calculated as the last of dates of attendance/last contact on Follow-up Report.

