7.9 Concomitant Medications and Other Anti-Cancer Treatments

Concomitant medication is defined as medication, other than protocol therapy, which is taken by patients any time on treatment or after end of treatment. Patients may also receive any other anti-cancer treatment during or after being taken off protocol treatment.

- Concomitant medications for patients during protocol treatment (reported on Chemotherapy Report, CRF Pre-Excision Report, and CRF Surgery Report) (**Table 46**)
- Concomitant medications for patients 30 days after excision (reported on CRF Follow-Up Report) (**Table 46**)
- Anti-cancer treatments for patients during protocol treatment (reported on Chemotherapy Report, CRF Pre-Excision Report, and CRF Surgery Report) (**Table 47**)
- Anti-cancer treatments for patients after protocol treatment but before relapse (reported on Follow-Up Report) (**Table 47**)
- Anti-cancer treatments for patients after relapse (reported on Short Follow-Up Report) (**Table 47**)

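### SAP 7.7.4 names the wrong source forms for the non-protocol-therapy DFS event: the Follow-Up Report is missing, and two listed forms cover only the time before DFS starts

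*SAP*

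**What the plan says.** Protocol 8.7 lists as a DFS failure, with no restriction on where it is recorded: "Non-protocol radiotherapy, chemotherapy or biologic therapy without documentation of the site of failure".

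SAP 7.7.4 sets the same time zero: "Disease-Free Survival (DFS) is defined as the interval from complete tumour surgical excision date". It ties this event to three forms: "Non-protocol radiotherapy, chemotherapy, or biologic therapy without documentation of the site of failure and reported in CRF Chemotherapy Report, Pre-Excision Report, and Surgery Report". In that section the Relapse Report is the source for locoregional and distant events only. The censoring sentence that follows mentions the same therapy but names no forms for it.

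SAP 7.9 says what each form records. The same three forms supply "Anti-cancer treatments for patients during protocol treatment (reported on Chemotherapy Report, CRF Pre-Excision Report, and CRF Surgery Report"). Later treatment comes from elsewhere: "Anti-cancer treatments for patients after protocol treatment but before relapse (reported on Follow-Up Report").

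Protocol Appendix III describes the Follow-Up Report as "Continued follow-up after chemotherapy, radiotherapy and/or protocol tumour excision(s) completed". It makes the Surgery Report due within 4 weeks after TME or TEMS/TAMIS, and requires a Relapse Report at relapse or failure.

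**The concern.** The form list does not match the period at risk. A DFS event can occur only after complete excision, yet two of the three listed forms describe time before it, and the form designed for the period after it is absent. The SAP therefore narrows an event that the protocol defines without such a limit.

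Two things follow. Non-protocol therapy begun during follow-up, with no documented site of failure, is not picked up as an event, so 3-year DFS would be too high. Non-protocol therapy recorded before excision meets the wording of the event but has no valid event time, and the SAP has no rule for it. Two programmers working from the same text could produce different DFS estimates for a named secondary efficacy endpoint.

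**Working it through.** **Plan's own figure.** The documents give no number or rate for this event. The design figures in protocol 13.3 concern organ preservation and do not depend on it. The check is therefore a comparison of texts, followed by the effect per event.

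**Step 1: forms against time at risk** (SAP 7.7.4 and 7.9; protocol Appendix III).

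| Form | Period covered | Listed for this event? | Can hold therapy started after complete excision? |
|---|---|---|---|
| Chemotherapy Report | each neoadjuvant cycle | yes | no |
| Pre-Excision Report | pre-excision visit | yes | no |
| Surgery Report | the operation; due within 4 weeks after it | yes | only early |
| Follow-Up Report | after treatment and excision | no | yes |
| Relapse Report | at relapse or failure | no (locoregional and distant only) | yes |

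**Step 2: how much of three years the list can reach.** With the SAP conversion of 30.4375 days per month, 36 months is 36 × 30.4375 = 1,095.75 days. A Surgery Report completed on its due date reaches day 28: 28/1,095.75 = 2.6% of the window. Suppose TME follows TEMS/TAMIS at the outer limit of 8 weeks, the clock started at TEMS/TAMIS, and the TME Surgery Report comes 4 weeks later. The reach is then 12 × 7 = 84 days, or 84/1,095.75 = 7.7%.

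**Step 3: two patients traced through the rules.**

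- *Patient A* starts non-protocol chemotherapy at month 12 with no documented site of failure, recorded on the Follow-Up Report. Protocol 8.7: failure. SAP event list: no event. SAP censoring sentence: not clearly censored either, because it sets aside patients given such therapy, whatever the form.
- *Patient B* has non-protocol therapy on the Pre-Excision Report. The form matches, but event date minus excision date is negative. The SAP does not say whether to ignore the therapy, count a failure or drop the record. Assume 50 patients, complete 3-year follow-up and 5 other events. Ignoring the therapy gives 45/50 = 90.0%, counting it gives 44/50 = 88.0%, and dropping the record gives 44/49 = 89.8%.

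**Step 4: effect of missed events.** With n patients fully followed, d true failures and k of them missed, the estimate is (n − d + k)/n, so the upward shift is k/n.

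- n = 50 (planned evaluable): 1/50 = 2.0 points; 3/50 = 6.0 points.
- n = 58 (all accrued): 1/58 = 1.7 points.

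The range of 1 to 3 missed events is an assumption.

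**Step 5: against precision.** The approximate 95% half-width is 1.96 × √(S(1 − S)/50). For assumed 3-year DFS of 0.80, 0.85 and 0.90 it is 11.1, 9.9 and 8.3 points. A shift of 2.0 to 6.0 points lies inside that, but it is a one-sided error that the confidence interval does not reflect.

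**The case against.** The strongest reply is that little is likely to be lost. DFS is descriptive, with no test attached. Protocol 8.7.1 requires a full work-up at first failure, so many patients given further therapy will have a documented site and enter as locoregional or distant events. Some of the rest should have a Relapse Report, since Appendix III requires one at failure. SAP Table 47 will show Follow-Up Report therapy in aggregate. The Surgery Report is completed after the operation, so it would be wrong to say that every listed form precedes excision. All of this stands and limits the size. None of it makes the list right: SAP 7.7.4 does not use the Relapse Report for this event, and Table 47 does not feed the DFS estimate.

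A reader might infer more: that chemoradiotherapy before TEMS/TAMIS would be scored both as an organ-preservation success and as a DFS failure. The documents do not support that. Protocol 7.1.1.1 and 7.2 say that patients who cannot tolerate FOLFOX "may receive preoperative 5FU chemoradiotherapy based on investigator decision", so on a plain reading this treatment is not non-protocol. Nor is TEMS/TAMIS after it a pathway the protocol sets out: 7.1.3.1 points such patients towards TME, and the table in 7.3 places radiotherapy only before TME. The primary endpoint counts ypT0/T1good N0 patients "who avoid radical surgery (TME) among all patients treated with FOLFOX or CAPOX and TEMS or TAMIS", with no condition on radiotherapy. There is no contradiction to repair there, and no case for an extra Table 30 row or a sensitivity analysis of the primary endpoint.

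One cost is real. Protocol 8.7 as worded also counts post-operative chemotherapy given without a documented failure, so adding the Follow-Up Report may bring such patients in as events.

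**Conclusion.** The concern holds as an internal inconsistency in the SAP. The source list for this event contradicts SAP 7.9, is narrower than protocol 8.7, does not fit the DFS time zero, and leaves some patients neither events nor clearly censored. Followed literally, it biases 3-year DFS upward by about 2 points per missed event. That size assumes 50 patients with complete 3-year follow-up. The number of missed events is unknown and may be zero. The upward direction assumes that the programmer follows the event list and treats unlisted cases as event-free. Organ preservation, its cut-off and its power are not affected.

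**What to change.** In SAP 7.7.4:

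1. Define the event as non-protocol radiotherapy, chemotherapy or biologic therapy started after the complete-excision date, without a documented site of failure.
2. Take it from the Follow-Up Report, the Relapse Report and, for therapy started after excision, the Surgery Report. Remove the Chemotherapy and Pre-Excision Reports.
3. State that radiotherapy or chemoradiotherapy given under protocol 7.1.1.1, 7.2 or 7.3 is not a DFS event. This also settles radiotherapy given between TEMS/TAMIS and TME.

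The cost is a few sentences of SAP text. No new data are needed, because SAP 7.9 shows that the Follow-Up Report already records anti-cancer treatment. Reported DFS may fall if post-operative chemotherapy without documented failure is now counted, as protocol 8.7 requires. Table 31 already lists non-protocol therapy by type, so readers can see how many events are of that kind.
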